Patients would have received their last dose of study drug in the pivotal phase 3 study on the day prior to the Week 24/Baseline visit and will receive their first dose of study drug for this extension study in the clinic after the patient is determined to be eligible for this extension study and has provided informed consent to participate. Therefore, results of testing required for eligibility must be available on or prior to the Week 24/Baseline visit. The administration of the first dose of study drug for MVT-601-3103 will define enrollment into this study. Patients will then take the open-label study treatment (relugolix 40 mg co-administered with estradiol 1 mg and norethindrone acetate 0.5 mg) orally once daily for 80 weeks. If necessary, for logistical reasons (eg, delayed availability of study drug supply on site, others), and with sponsor/designee approval, the first dose of open label study drug for MVT-601-3103 may be administered up to 10 days following the pivotal phase 3 study Week 24/Baseline visit. If the first dose of study drug is not given during this up to 10-day interval, the pivotal phase 3 study safety follow-up procedures should be followed (ie, adverse event reporting, electronic diary [eDiary] completion, etc.).

During the 80-week Open-Label Treatment period and the ~30-day Follow-Up period, patients will continue to record study treatment, assessment of pain using the NRS, menstrual bleeding, analgesic use, and the functional effects of endometriosis-associated pain (sB&B) in the eDiary during the time periods specified in the protocol. Only study-specific rescue analgesic medications should be used starting with the Week 24/Baseline visit and through the Follow-Up visit and these medications will be taken for control of pain and not prophylactically. Health-related quality of life questionnaires; PGIC for dysmenorrhea, NMPP, and dyspareunia; and PGA for pain and function will be completed during the visits on an electronic tablet, according to the study protocol Schedule of Activities (Section 1.1).

Safety will be assessed throughout the study by monitoring adverse events, vital signs and weight, physical examinations, clinical laboratory tests, 12-lead ECGs, mammograms (for women who are or become ≥ 40 years old during the study), endometrial biopsies, and bone mineral density with DXA.

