4.4.2. Adverse Events and Concomitant Medications

The following imputation rules for the safety analyses will be used to address the issues with partial dates. The imputed dates will be used to determine the treatment-emergent period. For adverse events with a partial date, available date parts (year, month, and day) of the partial date will be compared with the corresponding date components of the start date and end dates of the treatment-emergent period to determine if the event is treatment emergent. When in doubt, the adverse event will be considered treatment emergent by default.

The following rules will be applied to impute partial dates for adverse events:

- If start date of an adverse event is partially missing, impute as follows:
 - If both Month and Day are missing and Year = Year of extension study treatment start date, then set to extension study treatment start date, as long as adverse event end date is not prior to extension study treatment start date;
 - If both Month and Day are missing and Year \neq Year of extension study treatment start date, then set to January 1;
 - If Day is missing and Month and Year = Month and Year of extension study treatment start date, then set to extension study treatment start date, as long as adverse event end date is not prior to extension study treatment start date;
 - If Day is missing and Month and Year \neq Month and Year of extension study treatment start date, then set to first of the month;
 - If start date is completely missing, set to extension study treatment start date, as long as adverse event end date is not prior to pivotal phase 3 study treatment start date.
- If end date of an adverse event is partially missing, impute as follows:
 - If both Month and Day are missing, then set to December 31;
 - If only Day is missing, then set to last day of the month;
 - If end date is completely missing, do not impute.

When the start date or end date of a medication is partially missing, the date will be imputed to determine whether the medication is prior or concomitant (or both).

The following rules will be applied to impute partial dates for medications:

- If start date of a medication is partially missing, impute as follows:
 - If both Month and Day are missing, then set to January 1;
 - If only Day is missing, then set to the first of the month.
- If end date of a medication is partially missing, impute as follows:
 - If both Month and Day are missing, then set to December 31;

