9.1. Adverse Events

Adverse events will be collected from the time of the first dose of open-label study drug through the safety Follow up visit approximately 30 days after the last dose of open-label study drug (the end of extension treatment period), or the date of initiation of another investigational agent or hormonal therapy or surgical intervention affecting the hypothalamic-pituitary-gonadal axis or surgical intervention for endometriosis, whichever occurs first, as also specified in the Schedule of Activities in the study protocol Section 1.1. Additionally, serious adverse events reported to the investigator after the safety reporting period should be reported to the sponsor regardless of causal relationship to study drug treatment.

Using a Safety Report Form, all serious adverse events must be reported within 24 hours of the study site personnel's knowledge of the event, regardless of the investigator assessment of the relationship of the event to study drug.

The severity of all treatment-emergent adverse events will be evaluated by the investigator based on the National Cancer Institute's Common Terminology Criteria for Adverse Events (CTCAE, version 5.0 dated 27 Nov 2017), and will be coded to preferred term and system organ class using MedDRA 22.0 or higher.

A treatment-emergent adverse event is defined as any adverse event that occurs after administration of the first dose of pivotal phase 3 study drug.

Adverse event summaries will be based on treatment-emergent adverse events in the pivotal phase 3 and extension studies, unless otherwise specified. All adverse events in the pivotal phase 3 and extension studies will be listed in by-patient listings.

The following tabular summaries that include the number and percentage of patients will be provided:

- Overview of adverse events;
 - Safety parameters of interest

- Safety parameters of interest with first onset during extension study
- All adverse events;
 - By SOC and PT;
 - By decreasing frequency of PT;
 - By SOC, PT, and maximum severity;
 - Study drug-related per investigator by SOC and PT;
 - By time to onset (Day 1 to Week 24, > Week 24 to Week 52, >Week 52 to Week 78, > Week 78 to Week 104, > Week 104), SOC and PT;
 - Exposure-adjusted AE rate by SOC and PT
- Adverse events reported in at least 5% of patients in any treatment group
 - By decreasing frequency of PT;
- Grade 3 or above adverse events;
 - By SOC and PT;
 - By decreasing frequency of PT;

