 - Study drug-related per investigator by SOC and PT;
 - First onset events during extension study by decreasing frequency of PT
- Adverse events leading to study drug withdrawal;
 - By SOC and PT;
 - By decreasing frequency of PT;
- Adverse events leading to dose withdrawal with first onset during extension study;
 - By SOC and PT;
 - By decreasing frequency of PT
- Adverse events resulting in fatal outcome;
 - By decreasing frequency of PT;
- Serious adverse events;
 - By SOC and PT;
 - By SOC, PT and maximum grade
 - By decreasing frequency of PT;
 - By SOC, PT, and relationship to study drug;
- Adverse events of clinical interest (ALT or AST $\geq 3 \times$ ULN);
 - By SOC, PT, and maximum severity;

- By decreasing frequency of PT.
- First onset events during extension study by PT
- Resolved while on study drug treatment (ie, prior to the last dose date)
- Adverse events with first onset during the extension study;
 - By SOC and PT;
 - By decreasing frequency of PT;
- Serious adverse events with first onset during the extension study;
 - By SOC and PT;
- Mood disorder event with first onset during the extension study;
 - By decreasing frequency of PT;
 - Resolved while on study drug treatment (ie, prior to the last dose date)
- Vasomotor symptoms with First Onset During the Extension Study
 - By SOC and PT;
 - By decreasing frequency of PT;
 - Resolved while on study drug treatment (ie, prior to the last dose date)
- Bone health related events
 - By decreasing frequency of PT;
 - First onset events during extension study by PT;
- Hepatic transaminase elevations
 - By decreasing frequency of PT;
 - First onset events during extension study by PT;
- Carbohydrate and lipid metabolic effects
 - By decreasing frequency of PT;
 - First onset events during extension study by PT;

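### For a completely missing adverse event start date, SAP 4.4.2 imputes the extension start but checks the end date only against the pivotal start, so onset can fall after resolution

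*SAP*

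**What the plan says.** Section 4.4.2 lists the rules for incomplete adverse event start dates. Three of them impute the extension treatment start date, each with a condition on the end date.

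- Month and day missing, year equal to that of the extension start: imputed "as long as adverse event end date is not prior to extension study treatment start date".
- Day missing, month and year equal to those of the extension start: the same condition.
- Nothing known: "If start date is completely missing, set to extension study treatment start date", but "as long as adverse event end date is not prior to pivotal phase 3 study treatment start date".

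Pivotal-study events are in scope. Section 9.1 states: "Adverse event summaries will be based on treatment-emergent adverse events in the pivotal phase 3 and extension studies". It also anchors treatment emergence on the pivotal study: "A treatment-emergent adverse event is defined as any adverse event that occurs after administration of the first dose of pivotal phase 3 study drug". The section then plans outputs that depend on the onset date, including a group headed "Adverse events with first onset during the extension study" and a table "By time to onset (Day 1 to Week 24, > Week 24 to Week 52", continuing to beyond Week 104. Section 9.1.8 divides the number of patients with an event by exposure time among patients at risk of a first occurrence.

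**The concern.** A condition of this kind exists to stop the imputed start from passing the known end. It does so only if it tests the end date against the date being imputed. The two partial-date rules meet that requirement. The completely-missing rule tests against a date about 24 weeks earlier, so it lets through every event that ended during the pivotal treatment period.

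An event let through in this way is dated to Extension Study Day 1 although it was over before then. The outputs at stake are those that use the onset date:

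- the extension-onset tables (all events, serious events, Grade 3 or above, withdrawals, and the mood, vasomotor, bone, hepatic and metabolic groupings);
- the time at risk in the exposure-adjusted rates;
- possibly the time-to-onset table.

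Nothing else in 4.4.2 or 9.1 prevents a start date after the end date.

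**Working it through.** The plan gives no figure to reproduce. The check applies the rule as written to each possible end day and compares imputed start with end.

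**Inputs**
- Pivotal first dose = Study Day 1 (section 4.3.3).
- Extension first dose, taken as E = 169 or E = 179. Day 169 is the Week 24 target in Table 3, and dosing normally starts at that visit. Section 2.1 allows a delay: the first dose "may be administered up to 10 days following the pivotal phase 3 study Week 24/Baseline visit", so 169 + 10 = 179. These two values are illustrative; actual visit days vary.
- End day e, run from Day -30 to Day 731.

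**Rule as written:** impute start = E if e is missing or e ≥ 1. The result is impossible when E > e, that is, for 1 ≤ e ≤ E - 1.

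**Partial-date condition applied instead:** impute start = E if e is missing or e ≥ E. Start can then never exceed end.

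| Extension first dose | End days giving start after end, as written | With the partial-date condition |
|---|---|---|
| Day 169 | Days 1 to 168 (168 of 168) | 0 |
| Day 179 | Days 1 to 178 (178 of 178) | 0 |

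Example: e = 60. The imputed start is Day 169, which is 169 - 60 = 109 days after resolution, or 179 - 60 = 119 days with the delayed start.

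**Exposure-adjusted rates.** The true onset was no later than Day 60. If a patient's time at risk stops at first occurrence, she contributes at least 109 days too many in this example.

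**Time-to-onset interval.** The true onset lies in the first interval, apart from the extra days just before a delayed start. Whether the imputed start lies there too depends on the last day of that interval, which section 9.1 does not give. The SAP uses several days for Week 24 elsewhere:

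| Last day of first interval | Source of that day | E = 169 | E = 179 |
|---|---|---|---|
| 168 | Bleeding windows, section 9.3.7 | moves out | moves out |
| 169 | Target day, Table 3 | stays | moves out |
| 183 | Window end, Table 3 | stays | stays |

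The interval error is therefore conditional. The onset-after-end error is not.

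**The case against.** The best defence is that the imputed dates are said to serve the treatment-emergence decision, and that decision is anchored on the first pivotal dose. For that purpose the pivotal check sorts correctly: an event that ended before the pivotal start is not emergent, and any other is, with doubtful cases counted as emergent by default. This stands as far as it goes. It explains why someone might have written the pivotal date, and it means that the overall incidence tables are largely untouched. It does not rescue the imputed value, which is the extension start and which other planned tables use.

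A reader might go further and infer that a placebo event becomes a relugolix event. The SAP does not support that. Section 4.2.2 analyses safety by pivotal treatment group, and section 9.1.8 does the same for the exposure-adjusted rates. Group belongs to the patient and is not derived from the event date. Relatedness is the investigator's rating (section 9.1.1). The event of a former placebo patient stays in her column; what changes is that it is shown as arising in the open-label period.

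A reader might also infer that every affected record lands in the wrong time-to-onset interval. The second table above shows that this depends on an unstated boundary and on the day of first extension dose.

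Finally, the affected records may be few. Each needs a start date with not even a year, together with an end date, known or imputed, in the pivotal period. The SAP does not say whether any exist.

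**Conclusion.** The rule is wrong as written. Its condition does not match the date it imputes, and it produces an onset after resolution for every event with no start date that ended between the first pivotal dose and the day before the first extension dose. Each such record is dated to Extension Study Day 1 and can be counted falsely as arising in the extension, and its time at risk is overstated.

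The point is minor. Treatment-emergent totals and the treatment-group column are largely unaffected, the time-to-onset effect is conditional, and the number of records is unknown and may be zero.

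The conclusion rests on two readings. First, the rule is programmed literally across both studies, as the pooling in section 9.1 implies. Second, extension onset is decided by comparing the start date with the first extension dose; the SAP does not define that term in words.

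**What to change.** Replace the completely-missing bullet with three branches, using the end date after any end-date imputation:

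- (a) End date missing, or on or after the extension treatment start: set the start to the extension treatment start.
- (b) End date on or after the pivotal treatment start and before the extension treatment start: set the start to the pivotal treatment start.
- (c) End date before the pivotal treatment start: do not impute, and treat the event as not treatment emergent.

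Swapping the extension date into the existing condition is not enough, because events that fail it would have no rule. Sending all of those to the pivotal start is not enough either: an event that ended before pivotal Day 1 would again start after its end and could be counted as emergent. The pivotal check therefore has to remain, as the line between (b) and (c).

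The cost is a few lines of SAP text and a small programming change. No endpoint, data collection or population changes. A count of adverse event records with no start date and an end date before the extension start would show whether any output is affected.

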4.5. Handling Multiple Values on the Same Day

Questionnaires

If a questionnaire (eg, PGA, PGIC, or EHP-30) is completed multiple times on the same day, then the questionnaire assessment with the worst score will be used for analysis.

eDiary Entries

If there are multiple eDiary entries (NRS, sB&B) on the same day for a patient, then the worst score (eg, higher pain score) will be used for analysis.

If there are multiple eDiary entries (analgesics) reported on the same day but at different time for a patient, then all pills reported at different time will be used for analysis. If there are multiple eDiary entries (analgesics) on the same day and at the same time, then the record with the last modified time will be used for that time.

5. STUDY POPULATION

5.1. Subject Disposition

The number and percentage of patients for each of the following categories will be summarized by pivotal phase 3 study treatment group in final analysis:

- All patients enrolled defined as taking the first dose of study drug in the Extension Study;
- Patients included in the Extension Study population;
- Patients included in the Extension Safety population.

In final analysis, the number and percentage of patients for each of the following categories will be summarized by pivotal phase 3 study treatment group:

- Patients who completed 52 weeks treatment (24 weeks pivotal study treatment period and 28 weeks open-label treatment period)
- Patients who completed the 104 weeks of treatment (24 weeks pivotal study treatment period and 80 weeks open-label treatment period);

- Patients who discontinued early from the 80 weeks open-label treatment period and reasons for discontinuation;
- Patients who entered the BMD post-treatment Follow-Up period.

5.2. Protocol Deviations

Protocol deviations that occurred during the extension study will be categorized as important or minor per the most updated version of protocol deviation plan. Important protocol deviations will include, but will not be limited to, the following categories:

- Patient treated with open-label study drug who did not satisfy key entry criteria;
- Patient treated with open-label study drug who met withdrawal criteria during the study but was not withdrawn;
- Patient treated with open-label study drug who received a prohibited concomitant medication that met criteria for an important protocol deviation.

Important protocol deviations will be summarized by deviation category for all patients in the Extension Study Population. A patient listing of all important protocol deviations will be provided.

5.3. Demographic and Baseline Characteristics

Demographic and Baseline characteristics will be summarized by pivotal phase 3 study treatment group in Extension Study Population. Categorical data will be summarized using frequencies and percentages, by pivotal phase 3 study treatment group and overall (see [Table 12e 12](#)). Summaries of continuous data will display the mean, SD, median, minimum, and maximum. The numbers of missing values will also be summarized.

Table 12: Categories for Demographic and Baseline Characteristics

Variable	Category
Age (years)	< 35, ≥ 35
Geographic region	North America, Rest of World
Race	Black or African American, White, American Indian or Alaska Native, Asian, Native Hawaiian or Other Pacific Islander, Other
Ethnicity	Hispanic or Latino, Not Hispanic or Latino, or Not reported
BMI (kg/m ²)	< 18.5, 18.5 to <25, 25 to <30, 30 to < 35, 35 to < 40, ≥ 40
Time Since Surgical Diagnosis of Endometriosis (years)	< 5, ≥ 5 < 2, 2 to < 5, ≥ 5
Alcohol Consumption History	None, Moderate, Heavy

Smoking History	Never smoker, Former smoker, Current smoker
Analgesic Use (During Run-In Period in pivotal phase 3 study)	None, Tier 1 only, Tier 2 only, Both Tier 1 and Tier 2
Dysmenorrhea NRS Score	< 7, ≥ 7 < 4, 4 to < 7, 7 to 10
NMPP NRS Score	< 4, ≥ 4 < 4, 4 to < 7, 7 to 10
EHP-30 Pain Domain Score	0 to < 25, 25 to < 50, 50 to < 75, 75 to 100
Patient Global Assessments	
Dysmenorrhea	Absent, Mild, Moderate, Severe, Very Severe
NMPP	Absent, Mild, Moderate, Severe, Very Severe
Function	Not at all, Minimally, Moderately, significantly, very significantly
Overall Pelvic Pain	Absent, Mild, Moderate, Severe, Very Severe
American Fertility Society of Endometriosis Stage	I Minimal; II Mild; III Moderate; IV Severe; Unknown/Not Available
Bone Mineral Density	
Lumbar L1-L4	Mean (SD), median, min, max
Total Hip	Mean (SD), median, min, max
Femoral Neck	Mean (SD), median, min, max
Renal Function ^a	CrCl: < 60, ≥ 60 to < 90, ≥ 90 mL/min

Abbreviations: BMI = body mass index; CrCl = creatinine clearance; EHP-30 = Endometriosis Health Profile 30-Item Questionnaire; NMPP = non-menstrual pelvic pain; NRS = numerical rating scale; SD = standard deviation.

^a Creatinine clearance by Cockcroft-Gault Equation = $0.85 \times \{(140 - \text{age}(\text{years})) \times \text{weight}(\text{kg})\} / (72 \times \text{Serum Creatinine}(\text{mg/dL}))$ for women.

5.4. Medical History

Medical history collected at the time of entry into the pivotal phase 3 study will be coded using the Medical Dictionary for Regulatory Activities (MedDRA) and will be summarized by system organ class (SOC) and preferred term (PT) for the Extension Study Population. Additionally, summaries of endometriosis-specific medical history, and historic medical and surgical treatments collected at the time of entry into the pivotal phase 3 study will be provided. A patient with multiple occurrences of medical history within a PT will be counted only once in that PT.

5.5. Concomitant Medications

Concomitant medications taken during the extension study treatment period and overall treatment period will be summarized for all patients in the Extension Safety Population by pivotal phase 3 study treatment group. Medications are considered concomitant during the extension study if exposure starts prior to the pivotal phase 3 study and continues in the extension treatment period, or exposure starts during the pivotal phase 3 study and continues in

the extension treatment period, or exposure starts during the extension study and continues in the extension treatment period. Medications are considered as overall concomitant if exposure starts prior to the pivotal phase 3 study, starts during the pivotal phase 3 study, or starts during the extension study, with exposure ending in the pivotal phase 3 study period, ending in the extension treatment period, or continuing after the extension treatment period.

A patient who has been administered several medications with the same preferred medication name will be counted only once for that preferred medication name.

Certain medication types will be summarized separately, including Tier 1 analgesics, Tier 2 analgesics, all analgesics, hormonal contraceptives, estrogens, progestins, other hypothalamic-pituitary-gonadal axis affecting drugs, calcium supplements, vitamin D supplements, and glucocorticoids.

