4.3.5. Definition of Overall Treatment Duration

In the final analysis, overall treatment duration is defined as the duration of time from the date of the first dose of pivotal phase 3 study drug to the date of the last dose of extension study drug as follows:

$$(\text{Date of last dose of extension study drug} - \text{Date of first dose of pivotal phase 3 study drug}) + 1$$

For patients missing day and month of the last dose date of extension study drug, the last date extension study drug was dispensed will be used to calculate overall treatment duration. For patients missing only day for date of last dose of extension study drug, the later of first of the month of last dose of extension drug or last date extension study drug was dispensed will be used to calculate treatment duration.

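### The overall-concomitant rule in SAP Section 5.5 sets no first-dose bound, so drugs stopped in the pivotal run-in would be tabulated as used during treatment

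*SAP*

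**What the plan says.** Section 5.5 gives the scope first: "Concomitant medications taken during the extension study treatment period and overall treatment period will be summarized for all patients in the Extension Safety Population". Two definitions follow.

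- **Extension period.** The first branch reads "Medications are considered concomitant during the extension study if exposure starts prior to the pivotal phase 3 study and continues in the extension treatment period". The other two branches, for starts during the pivotal study and during the extension, carry the same requirement of exposure in the extension treatment period.
- **Overall.** The start condition reads "Medications are considered as overall concomitant if exposure starts prior to the pivotal phase 3 study, starts during the pivotal phase 3 study, or starts" and goes on to name the extension study as the third possibility. The end condition is "with exposure ending in the pivotal phase 3 study period, ending in the extension treatment period, or continuing after the extension treatment period".

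The nearest definition of the overall treatment span is in Section 4.3.5, where "overall treatment duration is defined as the duration of time from the date of the first dose of pivotal phase 3 study drug"; the span closes with the last extension dose. Table 12 in Section 5.3 has a row headed "Analgesic Use (During Run-In Period in pivotal phase 3 study", with Tier 1 and Tier 2 categories, so the pivotal study had a run-in and analgesic use was recorded in it. Section 4.4.2 imputes partial medication dates so that each drug can be classed as prior, concomitant or both, but the SAP never defines prior.

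**The concern.** The two definitions in Section 5.5 do different things. The extension-period rule tests overlap with treatment. The overall rule tests only whether the start and end fall in named stretches of the programme, and for the pivotal part it names the study period, whereas for the extension it names the treatment period. A study period that includes a run-in is longer than the treatment period, so a drug can satisfy the rule without having been taken alongside study drug.

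At stake is whether the overall medication tables show what their scope sentence promises. Section 5.5 tabulates separately several classes for which timing matters: Tier 1 and Tier 2 analgesics, hormonal contraceptives, estrogens, progestins, other drugs acting on the hypothalamic-pituitary-gonadal axis, and glucocorticoids. A woman whose only recorded use of such a class ended in the run-in would be counted as a user during treatment.

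**Working it through.** The SAP gives no figure for this rule, so there is none to reproduce. The check enumerates the cases.

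**Epochs, in order:** (1) before the pivotal study; (2) pivotal run-in; (3) pivotal treatment; (4) extension treatment; (5) extension follow-up after the last dose; (6) after the study. Epoch 2 comes from Table 12, epochs 3 and 4 from Sections 4.3.1, 4.3.2 and 4.3.5, and epoch 5 from Section 2.1, which describes a follow-up of about 30 days and BMD follow-up to 12 months, with concomitant medication recorded at the 6- and 12-month visits.

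**Number of cases:** a drug's end cannot precede its start, so there are 6 × 7 / 2 = 21 combinations.

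**Target:** overlap with treatment, meaning a start in epoch 4 or earlier and an end in epoch 3 or later.

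**Rule as written:** a start in epoch 5 or earlier, and an end in epoch 2 or 3 (pivotal study period), in epoch 4, or beyond epoch 4. The last option was read in two ways: literally, as any exposure after the extension treatment period; and strictly, as requiring the drug to be in use already when treatment ends.

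| Start | End | Overlaps treatment | Overall rule, literal | Overall rule, strict | Extension rule |
|---|---|---|---|---|---|
| Before pivotal study | Run-in | No | Counted | Counted | Not counted |
| Run-in | Run-in | No | Counted | Counted | Not counted |
| Follow-up | Follow-up | No | Counted | Not counted | Not counted |
| Follow-up | After study | No | Counted | Not counted | Not counted |

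The other 17 combinations are classified correctly on both readings. There are therefore 4 of 21 mismatches on the literal reading and 2 of 21 on the strict one. The two run-in rows remain under both. These are counts of combinations and say nothing about how many patients fall in each.

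**Direction:** every mismatch is a drug counted that should not be. The rule can inflate a class row but cannot deflate it.

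**Size for a class row:** reported share − share with use during treatment = share of women whose only qualifying use of that class ended in the run-in (plus, on the literal reading, those whose only use began after the last dose). The SAP gives no data for these shares.

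**After the fix:** the overlap condition equals the target, so mismatches fall to 0 of 21.

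**The case against.** The strongest reply is that the intent is clear. The opening sentence of Section 5.5 limits the table to the treatment period, Section 4.4.2 distinguishes prior from concomitant drugs, and the pivotal study period may be loose shorthand for the pivotal treatment period, a term that Section 5.1 uses. The intent is indeed visible, but it does not repair the rule: the operative sentence says something else, the prior class has no definition, and so no first-dose boundary is available from elsewhere in the SAP.

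A reader might also infer that drugs first taken after the last dose will certainly be tabulated. The document does not support that. A drug that continues after a period was, in ordinary usage, already being taken when the period ended, and Section 9.3.5 sends medication from the post-treatment follow-up to a by-patient listing. That section does not expressly exclude such drugs from the overall table, so an ambiguity remains, but no more.

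A reader might further infer that the pain, bleeding or BMD results are compromised. They are not. Responder status and the analgesic-free and opioid-free proportions use eDiary records within pain assessment periods (Sections 7.2.3, 7.2.4 and 7.3.3). The BMD models and subgroups (Section 9.3.5) and the bleeding and amenorrhea analyses (Sections 9.3.7 and 9.3.8) use no concomitant-medication flag. The safety follow-up windows in Tables 3 and 9, and adverse event collection in Section 9.1, refer to the date another hormonal therapy begins, not to this flag. The SAP plans no confounding analysis based on these tables.

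**Conclusion.** The rule is wrong as written, within a narrow scope. It contradicts the opening sentence of its own section and differs from the adjacent extension-period rule, and it would count drugs stopped in the pivotal run-in as used during treatment. This rests on two readings: that the overall treatment period starts at the first pivotal dose, as Section 4.3.5 implies, and that the run-in belongs to the pivotal study, as Table 12 states. The possible inclusion of drugs begun after the last dose depends on how the end condition is read and should be treated as an ambiguity to settle.

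Only the descriptive overall concomitant-medication tables are affected, in a study with no formal comparisons. The number of women misclassified cannot be derived from the document. It also depends on whether run-in rescue analgesics enter the medication dataset with an end date before the first dose, which the SAP does not say. The point is worth correcting because a stated rule would give a wrong table, but it bears on no endpoint.

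**What to change.** Replace the overall-concomitant sentence in Section 5.5 with an overlap condition: start date on or before the date of last extension dose, and end date on or after the date of first pivotal dose, or ongoing. Sections 4.3.1 and 4.3.2 already define both dates, and the partial-date rules in Section 4.4.2 can be applied unchanged. This closes the run-in gap and settles the post-last-dose ambiguity together. Separate tables of prior and post-treatment medication are optional and not needed to correct the error. The cost is one sentence and one derived flag in the medication dataset, with no new data collection.
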